Agent(s)/Supplier: Targretin® (bexarotene) gel 1% / Valeant Pharmaceuticals

NCI Contract # HHSN261201200034I

Protocol Version Date: 4/27/2021

**Protocol Revision or
Amendment #** Version 14

SCHEMA

A Phase I Dose Escalation Study of Topical Bexarotene in Women at High Risk for Breast Cancer

Part 1: Dose Escalation Group

Screening/Baseline Clinic Visit Day -30 to 0

Women with ADH, ALH, LCIS, Breast cancer survivors (DCIS or invasive) ≥ 5 years from their diagnosis, BRCA 1/2 mutation carriers, or elevated risk for breast cancer $\geq 1.7\%$ in 5 years or lifetime risk $\geq 20\%$

Intervention (N=30) Dose Assignment by a 3+3 dose escalation with 3 dose levels (Day 0):

Bexarotene 1% gel 10mg/breast/every other day or Bexarotene 1% gel 10mg/breast/daily or Bexarotene 1% gel 20mg/breast/daily for treatment duration of 4 weeks

Start Treatment (Day 1)

Phone Call (Day 8)

Assess AEs and review Gel Diary

Study Visits (Day 15 and Day 28 (End of Study))

Assess for AEs & review gel diary. Labs to assess safety (CBC, LFTs, Lipid Profile, Thyroid Function Tests, Calcium) on Day 15 and 28 visits. Serum bexarotene collected on Day 0 and Day 28 visit. Optional breast biopsy at Day 28 visit.

Follow Up Call (30 days \pm 7 days after Day 28)

Assess for any further AE and document resolution of any acquired AE during treatment

Primary Endpoint: Safety and Toxicity

Secondary Endpoints: Serum and Tissue Bexarotene level, calcium, lipid and thyroid function biomarkers

Part 2: Dose Expansion Group

Screening/Baseline Clinic Visit Day -30 to 0

Women with ADH, ALH, LCIS, Breast cancer survivors (DCIS or invasive) that are ≥ 5 years from their diagnosis, BRCA 1/2 mutation carriers, or elevated risk for breast cancer $\geq 1.7\%$ in 5 years or lifetime risk $\geq 20\%$

Intervention (N=10) (Day 0):

Bexarotene 1% gel at maximum tolerated dose from Part A Dose Escalation Group for 4 weeks.

Start Treatment (Day 1)

Start application of bexarotene gel to one unaffected breast

Phone Call (Day 8)

Assess adverse events and review Gel Diary

Study Visits (Day 15 and Day 28 (End of Study))

Assess for AEs & review gel diary. Labs to assess safety (CBC, LFTs, Lipid Profile, Thyroid Function Tests, Calcium) on Day 15 and 28 visits. Serum bexarotene collected on Day 28 visit. Mandatory breast biopsy at Day 28 visit.

Primary Endpoint: Safety and Toxicity

Secondary Endpoints: Serum and Tissue Bexarotene level, calcium, lipid and thyroid function biomarkers

1. OBJECTIVES

The overall objective is to evaluate the safety and toxicity of topical bexarotene 1% gel to the breast in healthy women at high risk for breast cancer and bexarotene concentration in the breast tissue.

1.1 Primary Objectives

A. Dose Escalation Group

We will conduct a trial to determine the recommended phase II dose of topical bexarotene 1% (w/w) gel for evaluation in healthy women. This will be determined by assessing the safety and toxicity of topical bexarotene gel application (tested at three different dose levels by dose escalation, 10 mg (1 mL) every other day, 10 mg (1 mL) daily, or 20 mg (2 mL) daily to an unaffected breast of healthy women at high risk for breast cancer for a duration of 4 weeks.

B. Dose Expansion Group

We will conduct an intervention of topical 1% bexarotene gel to an unaffected breast of healthy women at high risk for breast cancer for 4 weeks at the maximum tolerated dose (MTD) as determined during the dose escalation group phase to assess bexarotene concentration in the breast tissue.

1.2 Secondary Objectives

1. To detect bexarotene concentration in the serum at baseline and at 4 weeks of treatment.
2. To detect bexarotene concentration in the breast tissue at 4 weeks of treatment in the dose escalation group.
3. To investigate the effects of topical bexarotene on serum biomarkers we will determine the change from the baseline in:
 - i. Lipid Biomarkers (Total Cholesterol, triglycerides, LDL, HDL)
 - ii. Thyroid Function Biomarkers (Thyroid Stimulating Hormone (TSH), T4, T3)
 - iii. Calcium

1.3 Exploratory Objective (Dose Expansion Group)

To examine changes in gene expression associated with retinoid action.

2. BACKGROUND

2.1 Breast Cancer Prevention

Breast cancer is the most common malignancy among women in the US, and prevention of this disease is therefore a major public health concern. Chemoprevention with anti-estrogens, including tamoxifen, raloxifene, and exemestane, has been shown to reduce the incidence of hormone receptor (HR)-positive breast cancer. However, agents that can reduce the incidence of hormone receptor negative breast cancer are currently lacking.

2.2 Bexarotene

Retinoids are vitamin A analogues that have been shown to be involved in cell differentiation, growth, and apoptosis (1). They exert their effects by binding to two specific classes of receptors known as the retinoic acid receptors (RAR) and retinoic X receptors (RXR). Once activated, RARs and RXRs form heterodimers and function as transcription factors and subsequently bind to retinoic acid response elements (RARE) and regulate

gene expression regulating cell differentiation, growth, and apoptosis (2, 3). Retinoids are similar agents but only activate the RXR receptors without activating the RAR nuclear receptors. Bexarotene is a retinoid that has been studied extensively and is currently an FDA approved treatment for cutaneous T cell lymphoma (CTCL).

Oral bexarotene was evaluated in phase 2 and 3 clinical trials for refractory or persistent early stage CTCL. Duvic et al. randomized 58 patients to two doses of bexarotene at 6.5mg/m² per day and 650mg/m² per day which was later modified to 300mg/m² per day for at least 16 weeks or until progression. Responses of greater than 50% improvement in skin lesions were noted in 20% of patients at 6.5mg/m² and 54% of patients had a response at 300mg/m² and 67% of patients at doses greater than 300mg/m². Seventy-three percent of patients that crossed over from 6.5mg/m² to higher doses responded with the increased dose. Hypertriglyceridemia, hyperlipidemia, headache, and hypothyroidism were noted in a significant number of patients and were reversible with discontinuation of drug. Since increased toxicity was noted at dose level greater than 300mg/m², recommended dose is 300mg/m² in patients with refractory CTCL (4).

Bexarotene has been developed as a gel and has been evaluated in clinical trials in patients with early stage CTCL. Based on the positive results of these studies, topical bexarotene is currently an FDA approved drug for the treatment of CTCL. In phase I and II trials conducted by Breneman and colleagues, topical bexarotene was applied to the skin lesions directly at different concentration levels of 0.1%, 0.5%, and 1% bexarotene gel. Patients started at the lowest concentration and applied the gel to affected skin lesions daily and titrated to twice daily dosing after 2 weeks and were tolerating the medication. As patients were able to tolerate gel application, bexarotene concentration was increased to 0.5% and then 1% and applying gel up to 4 times daily if tolerated. Most patients were able to tolerate 1% gel at twice daily dosing. The total dosage each patient received depended on the size and the number of lesions. Bexarotene gel was well tolerated and the most frequent adverse events in 67 patients were rash (73%), pruritus (33%), and pain (24%) with most being mild to moderate in severity. Systemic concentrations of bexarotene were extremely low and systemic side effects noted with oral bexarotene such as hyperlipidemia, hypothyroidism, and hypertriglyceridemia were not detected when medication was applied topically(5). Bexarotene 1% gel was also evaluated in a Phase I/II trial for alopecia areata and was applied to half of participants' scalp to assess response. Out of 42 patients, 31 (73%) experienced some dermal irritation with only 4 patients experiencing grade 3 dermal irritation. Most common adverse event noted was mild erythema in the area of treatment that resolved with discontinuation of the drug (6).

2.3 Rationale

In preclinical mouse models that develop ER-negative breast cancers, bexarotene showed significant activity in delaying mammary tumor development. In p53-null mice, bexarotene was given at 10mg/kg and 100mg/kg by gastric gavage and a 75% reduction in mammary tumor development was found in virgin mice at the higher dose level (7). In mouse mammary tumor virus (MMTV)-ErbB2 transgenic mice, focal tumors develop at eight months. Similar to humans, (MMTV)-ErbB2 mice undergo a multistage process of mammary tumorigenesis that progresses from normal mammary tissue to hyperplasia, mammary intraepithelial neoplasia (MIN) and finally invasive cancer. Li and colleagues gave bexarotene at 100mg/kg by oral gavage for 2 to 4 months in MMTV-erbB2 transgenic mice starting at three months of age. They found that bexarotene prevented the development of premalignant mammary lesions such as hyperplasia and MIN that is similar to human ductal carcinoma in situ (8).

Based on these preclinical findings, oral bexarotene at 200mg/m² has been evaluated in women at high risk for breast cancer based on their genetic risk. Bexarotene was found to reduce cyclin D1 RNA expression in breast cells from postmenopausal women (9). A nonsignificant reduction in Ki-67 expression was also seen in these post-menopausal women. Significant systemic side effects such as hypertriglyceridemia, hypercholesterolemia, and hypothyroidism were also found and were reversible after discontinuation of the drug(9). These results demonstrated that bexarotene has a biological effect on breast cells in women at high risk of breast cancer.

In addition to repressing cyclin D1 in breast cancer cells, bexarotene has shown effects on cyclin D1 in lung cancer cell lines. Dragnev et al. showed that the combination of bexarotene 1-4 μ mol/L plus erlotinib 1-4 μ mol/L significantly decreased cyclin D1 expression in cyclin-E- and KRAS/p53-driven transgenic lung cancer cell lines. The combination of bexarotene 400mg/m² per day plus erlotinib 150mg daily was evaluated in early stage non-small cell lung cancer patients in a window of opportunity trial and significant decreases in cyclin D1 were noted as well as an induction of necrosis and inflammatory responses (10).

Topical Therapies in Chemoprevention

Uptake has been low in chemoprevention medications such as tamoxifen and raloxifene due to its systemic side effects of menopausal symptoms and blood clots. Topical creams applied directly to the breast could affect the breast tissue without leading to systemic side effects. Mauvais-Jarvis and colleagues evaluated trans-4-hydroxytamoxifen (4-OHT), an active metabolite of tamoxifen, by topical administration to the breast. They evaluated 4-OHT absorption through the skin and its metabolism. Topical 4-OHT was applied directly over the breast in patients with invasive breast cancer and subsequently underwent mastectomy for their tumor. Concentration of 4-OHT was evaluated in breast tissue cytosol as well as nuclear extract and plasma samples taken at the time of surgery. 4-OHT was detected in the cytosol as well as in the nuclear extract as early as 24 hours of application and decreased in concentration over time at 7 days after application. Plasma concentrations of 4-OHT was low but 4-OHT metabolites were present in the plasma but not detected in the breast tissue. This showed that topical application bypassed the first pass hepatic metabolism of the drug. Mauvais- Jarvis *et al.* also evaluated the topical application of 4-OHT on the breast versus the abdomen and found retention of the drug in the breast and delayed plasma concentrations of 4-OHT when compared to application on the abdomen (11).

Rouanet *et al.* evaluated 4-OHT in a pre-surgical trial of 55 postmenopausal women with invasive ER positive breast cancer. Patients applied 4-OHT for 2 to 3 weeks at various dose levels compared to another group receiving oral tamoxifen at 20mg/day. They found that tissue proliferation decreased as measured by Ki-67 levels between baseline and after treatment. There was a significant decrease in proliferation in the topical treatment arms with lower plasma concentrations of tamoxifen compared to oral treatment (12). Lee and colleagues evaluated 4-OHT in women with DCIS for 6 to 10 weeks prior to surgery. Women were randomized to either 4-OHT (4mg/day) or oral tamoxifen (20mg/day) and assessed change in Ki-67 in their DCIS lesions. Tissue concentration of drug was similar between 4-OHT and oral tamoxifen whereas systemic concentrations of 4-OHT were lower than oral tamoxifen. Changes in proliferation were also similar across both arms. No serious adverse events were noted with 4-OHT in this study. Bexarotene is similar to retinoids and thus more likely to have skin reactions than 4-OHT (13).

We hypothesize that topical bexarotene can be applied to the breasts as a chemoprevention agent with penetration to the breast tissue and without having high systemic levels of drug and subsequent side effects and toxicity as seen with oral bexarotene. Data from chemoprevention studies with topical tamoxifen support the concept of topical agents penetrating into the breast tissue and exhibiting biological activity in the tissue. Preclinical models have clearly shown the effect of bexarotene in reducing the incidence of estrogen receptor negative breast cancer. Based on this data, we propose a phase I study to evaluate topical bexarotene in women at elevated risk for developing breast cancer.

Rationale for including Alcohol and Tobacco Assessment Questionnaires

Increasing evidence suggests that tobacco and alcohol use are risk factors in the development of intraepithelial neoplasia and cancer. In addition, tobacco and alcohol use may adversely affect agent intervention, for example by altering the safety profile or metabolism of a drug. Standardized assessments of tobacco and alcohol use during clinical trials will aid in understanding the potential relationship between the use of these products and clinical endpoints or cancer prevention biomarkers. Therefore, NCI, DCP is including assessment of tobacco and alcohol use at baseline and (include follow-up timepoint), to determine the potential impact of tobacco and

[figure not shown]
alcohol use on 1) treatment toxicity and symptom burden, and 2) the efficacy of treatment intervention.

3. SUMMARY OF STUDY PLAN

A. Dose Escalation Group

We will recruit women at high risk for breast cancer to this phase I study. We will use topical bexarotene 1% gel and this will be applied to one unaffected breast for 4 weeks. Participants will be assigned to one of three different dose levels. Bexarotene gel volume is estimated to be 1ml for 1g of gel which contains 10mg of bexarotene. Therefore, the three dose cohorts will be 10mg (1ml) every other day, 10mg (1ml) daily, 20mg (2ml) daily. Dose Limiting Toxicity (DLT) is defined as a grade 2 skin adverse event that persists for at least 6 days or any grade 3 or greater adverse event possibly, probably, or definitely related to the study drug. In addition, a DLT will be a grade 2 skin adverse event that recurs and persists for at least 3 days. A conservative modification of the standard “3+3” design will be applied. The first three participants will be assigned to the lowest dose level. New cohorts of 3-4 participants will not be treated until toxicity has been evaluated for all current participants for 4 weeks. Group assignment algorithm is explained in Section 13.4 and dose escalation is illustrated in Figure 1. The Maximum Tolerated Dose (MTD) will be defined as the highest dose level with at most 2 participants with DLT in 10 participants treated.

Figure 1: Dose Escalation Schema for Bexarotene 1% gel

Bexarotene gel will be provided by Valeant pharmaceuticals and repackaged by DCP pharmacy in dose metered pumps for dispensing the correct dose for application. Participants will begin application of the gel to the upper outer and upper inner quadrants of one breast every other day for one week and then increase to daily for 3 weeks if they are assigned to daily dosing arm. If participants are assigned to every other day dosing, they will continue in this manner for the entire 4 weeks. Participants that are assigned to 20 mg (2ml) daily will first start with application of 10mg (1ml) to the breast every other day for 1 week, then increase to 10mg (1ml) daily for 1 week, and then increase to 20mg (2ml) daily for the remaining 2 weeks as long as it is tolerated. Participants can also participate in an optional core breast biopsy of the upper outer or inner quadrant at the end of study treatment and receive compensation for additional expenses associated with the biopsy, such as additional travel expenses, time missed from work or other expenses associated with the biopsy visit. All participants will need

to come in for clinic visits for toxicity assessment and blood collection. All participants will receive a follow-up phone call from the site investigator or designee 30 days \pm 7 days after completion of study drug to assess for any further AE and document resolution of any acquired AE during treatment.

As of Oct 2019, enrollment was completed to the first dose cohort and the second dose cohort was stopped early due to DLTs. No DLTs were experienced in the first dose cohort of 10 patients that applied 10mg of bexarotene to the breast every other day. In the second dose cohort, participants applied 10mg daily after tolerating application of every other day for one week. Four participants were enrolled in this cohort and 1 participant withdrew early due to adverse events unrelated to study drug. Two DLTs were noted in the remaining patients and thus enrollment was stopped at the second dose level. Therefore, no patients will be enrolled to the third dose level due to concerns for toxicity. MTD is 10mg/breast/every other day.

B. Dose Expansion Group

A dose expansion group of additional 10 participants will be enrolled and treated at the MTD to further evaluate safety and drug penetration into the breast tissue. There will be a ramp up to the desired dose similar to the ramp up schedule in the dose escalation group. At any time in the dose expansion cohort, if there are $\geq 30\%$ DLT among participants, the trial will be terminated. Assessment for dose limiting toxicities will occur continuously as participants are enrolled into the dose expansion group. This will be determined after the third and each successive participant until 10 participants are in the group. Participants in this group will receive treatment for 4 weeks and undergo the same schedule of events as the dose escalation group. All participants in the dose expansion cohort will have a core breast biopsy at end of treatment and receive compensation for additional expenses associated with the biopsy, such as additional travel expenses, time missed from work or other expenses associated with the biopsy visit. All participants will receive a follow-up phone call from the site investigator or designee 30 days \pm 7 days after completion of study drug to assess for any further AE and document resolution of any acquired AE during treatment.

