Once MTD is identified, we will enroll another 10 participants into MTD and these participants will have mandatory biopsies before and after 4 weeks of treatment. We will continuously monitor aggregate DLTs in these participants together with the 10 participants treated during the dose escalation part of the study. If at any time the posterior probability of observing a DLT rate of at least 20% exceeds 70%, i.e., $\Pr(\text{DLT rate} \geq 0.20 | \text{Data}) > 70\%$, given the prior of the DLT rate of beta (0.2, 0.8), we will stop the trial and claim the dose is too toxic. Given the above rule, the boundaries for early stopping due to excessive DLT are Total Number of Participants with DLTs/Total Number of Participants $\geq 4/11\sim 14$, $5/15\sim 19$, and $6/20$. Combining with the boundaries during dose escalation phase, i.e., stop accrual at the dose level if Total Number of Participants with DLTs/Total Number of Participants $\geq 2/3$, $2/6$, $3/10$, $4/11\sim 14$, $5/15\sim 19$, and $6/20$, the early stopping probability for this level will be 15%, 51%, 82% if the true DLT rate is 0.10, 0.20, and 0.30, respectively.

Given that there are 3 dose levels and 10 participants enrolled at each level, and 10 additional participants at MTD, it is anticipated that 40 participants will be enrolled and treated and up to 40 will be evaluable at the end of this study.

Skin Toxicity

CTCAE criteria will be utilized to grade adverse events. Skin adverse events are expected to be the most common in this study. Bexarotene is similar to retinoids and retinoid dermatitis is very common and can be managed with temporarily withholding drug and restarting at a decreased frequency until tolerated by the individual. Dose modifications for each dose level have been defined in Section 5.5 to guide management of participant experiences of an adverse event

CTCAE criteria for skin will be modified (Table 3) for this study as adverse events are expected to be localized to the breast area. This modified criteria was also utilized by Talpur *et al.* when they evaluated bexarotene 1% gel on the scalp of participants with alopecia areata (6). Please see Table 3 for modified CTCAE criteria. Use plain language when talking to the participant about skin AEs. Refer to Appendix G for a plain language guide to support both phone and in-person assessments of skin application AEs.

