13.4 Primary Objective, Endpoint(s), Analysis Plan

The primary objective of this study is to determine the safety and toxicity of topical 1% bexarotene gel application to the breasts of healthy women at high risk for breast cancer for a duration of 4 weeks. Women with ADH, ALH, LCIS, breast cancer survivors (DCIS or invasive) ≥ 5 years from their diagnosis, BRCA 1/2 mutation carriers, and women with elevated risk for breast cancer $\geq 1.7\%$ in 5 years or lifetime risk $\geq 20\%$ will be recruited. Three dose levels are considered (10mg every other day, 10mg daily, and 20mg daily). Dose Limiting Toxicity (DLT) is defined as a grade 2 skin adverse event that persists for at least 6 days or any grade 3 or greater adverse event possibly, probably, definitely related to the study drug. In addition, a DLT will be a grade 2 skin adverse event that recurs and persists for at least 3 days. A conservative modification of the standard “3+3” design will be applied. The first cohort of 3 participants will be treated at the first dose level (10mg every other day). New cohort of participants will not be treated until toxicity has been fully evaluated for all current participants for 4 weeks. We will add another 4 participants when only 1 or less participants experience DLT in 6 treated participants. We will only escalate dose to the next higher level when 20% or less of total participants experience DLT. At any dose level, the algorithm is as follows:

- (1) If 0 or 1 out of 3 participants experience DLTs ($\leq 1/3$), an additional cohort of 3 participants will be treated at the same dose level. If total number of participants experiencing DLT at that dose level is 1 or less out of 6 ($\leq 1/6$), we will enroll another 4 participants the same dose level.
- (2) If at any time 2 or more participants experiences DLTs in 3 or 6 participants ($\geq 2/3$ or $\geq 2/6$) or 3 or more participants experience DLT in 10 participants ($\geq 3/10$), then the dose escalation will stop, and the next lower dose will be considered as the maximum tolerated dose (MTD).
- (3) In 10 participants at each dose level, if we observe 2 or less DLTs, a cohort of 3 participants will be treated at the next higher level. If 3 or more in 10 participants experience DLT, we will stop accrual to that level and above, and claim the regimen as to be too toxic for that level or above.

MTD is defined the highest dose level with at most 2 participants with DLTs in 10 participants treated.

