Once MTD is identified, we will enroll another 10 participants into MTD and these participants will have mandatory biopsies before and after 4 weeks of treatment. We will continuously monitor aggregate DLTs in these participants together with the 10 participants treated during the dose escalation part of the study. If at any time the posterior probability of observing a DLT rate of at least 20% exceeds 70%, i.e., $\Pr(\text{DLT rate} \geq 0.20 \mid \text{Data}) > 70\%$, given the prior of the DLT rate of beta (0.2, 0.8), we will stop the trial and claim the dose is too toxic. Given the above rule the boundaries for early stopping due to excessive DLT are Total Number of Participants with DLTs/Total Number of Participants $\geq 4/11\sim 14$, $5/15\sim 19$, and $6/20$. Combining with the boundaries during dose escalation phase, i.e., stop accrual at the dose level if Total Number of Participants with DLTs/Total Number of Participants $\geq 2/3$, $2/6$, $3/10$, $4/11\sim 14$, $5/15\sim 19$, and $6/20$, the early stopping probability for this level will be 15%, 51%, 82% if the true DLT rate is 0.10, 0.20, and 0.30, respectively.

Given that there are 3 dose levels and 10 participants enrolled and treated at each level, and 10 additional patients at MTD, it is anticipated that 40 participants will be treated and up to 40 will be evaluable at the end of this study.

At the end of the study, the toxicity data will be summarized for each dose level using frequency tabulation. The compliance of treatment application for each dose level will be presented using descriptive statistics.

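### Section 3 and Sections 8.1/13.4 set different DLT stopping rules for the same 10-woman expansion cohort, and nothing says which one governs

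*Combined protocol and SAP*

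**What the plan says.** Section 3, part B (Dose Expansion Group), gives a raw-proportion rule: "At any time in the dose expansion cohort, if there are $\geq 30\%$ DLT among participants, the trial will be terminated". Its look schedule follows: "This will be determined after the third and each successive participant until 10 participants are in the group".

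Sections 8.1 and 13.4 give a Bayesian rule on a different denominator: "We will continuously monitor aggregate DLTs in these participants together with the 10 participants treated during the dose escalation part of the study". With a Beta(0.2, 0.8) prior, if the posterior probability of a DLT rate of at least 0.20 exceeds 70%, then "we will stop the trial and claim the dose is too toxic". The listed boundaries are 4/11–14, 5/15–19 and 6/20. Combined with the escalation boundaries (2/3, 2/6, 3/10), Section 13.4 says that "the early stopping probability for this level will be 15%, 51%, 82% if the true DLT rate is 0.10, 0.20, and 0.30, respectively".

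Section 3 points to the statistical section for one purpose only: "Group assignment algorithm is explained in Section 13.4". Section 13.9 says that interim analysis is continual under the modified 3+3 design and names neither rule. Section 3 also reports the escalation result at the dose being expanded: "No DLTs were experienced in the first dose cohort of 10 patients that applied 10mg of bexarotene to the breast every other day".

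**The concern.** Both rules are current text, both end the trial, and both cover the same 10 women. They differ in denominator (expansion only, or expansion plus escalation), in criterion (observed proportion, or posterior probability) and in first look (third expansion participant, or pooled n = 11). A team working from Section 3 and a team working from Section 13.4 could therefore reach opposite decisions on the same data.

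Two things are at stake.

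- **Conduct.** Under Section 3, one DLT in the first three women ends a cohort whose stated objective in Section 1.1 is tissue concentration. Under Section 13.4 the team would carry on, and so go past a point at which Section 3 requires termination. The same 1/3 in escalation leads to more accrual at that dose: "If 0 or 1 out of 3 participants experience DLTs ($\leq 1/3$), an additional cohort of 3 participants will be treated".
- **Reported design properties.** The stated stopping probabilities describe the level as a whole but do not include the Section 3 trigger.

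**Working it through.** **Inputs.** Section 3: stop at a DLT proportion of at least 30%, looks at expansion n = 3 to 10. Sections 8.1/13.4: prior Beta(0.2, 0.8), threshold rate 0.20, cut-off 0.70, pooled looks at n = 11 to 20. Escalation looks: 2/3, 2/6, 3/10. Observed in escalation at this dose: 0/10 (Section 3).

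**Step 1. Reproduce the plan's boundaries.** With x DLTs in n women the posterior is Beta(0.2 + x, 0.8 + n − x). The boundary is the smallest x with Pr(rate ≥ 0.20) > 0.70.

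- 3/11 gives 0.671 (continue); 4/14 gives 0.740 (stop)
- 4/15 gives 0.692 (continue); 5/19 gives 0.711 (stop)
- 5/20 gives 0.669 (continue); 6/20 gives 0.831 (stop)

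This confirms 4/11–14, 5/15–19 and 6/20.

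**Step 2. Reproduce the plan's stopping probabilities.** Exact binomial recursion: carry the probability of each DLT count forward one woman at a time, removing the mass at or above the boundary at n = 3, 6, 10 and 11 to 20. Result: 0.150, 0.513 and 0.823 at true rates 0.10, 0.20 and 0.30, matching the stated 15%, 51% and 82%.

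**Step 3. Put both rules on the expansion scale, given 0/10.** Section 3 stops at the smallest whole number not below 0.3n.

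| Expansion women evaluated | Section 3 stops at | Pooled rule stops at |
|---|---|---|
| 3 | 1 | not reachable |
| 4 | 2 | 4 |
| 5–6 | 2 | 5 |
| 7–9 | 3 | 5 |
| 10 | 3 | 6 |

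One DLT in 3 is 1/13 pooled (posterior 0.080). Three in 10 is 3/20 pooled (posterior 0.243). Section 3 terminates at both; the pooled rule stops at neither.

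**Step 4. Probability of stopping in the expansion, given 0/10** (same recursion).

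| True DLT rate | Section 3 | Pooled rule |
|---|---|---|
| 0.05 | 15% | 0.004% |
| 0.10 | 30% | 0.1% |
| 0.20 | 58% | 2.0% |
| 0.30 | 79% | 10.0% |

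At a rate of 0.10 the look at three women alone fires with probability 1 − 0.9³ = 0.271. Averaged over the protocol's own prior updated with 0/10, Beta(0.2, 10.8), the stopping probabilities are 5.4% and 0.08%.

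**Step 5. Whole level, before any data, if both triggers apply.** Enumerating all 2¹⁰ = 1,024 expansion sequences after 0, 1 or 2 escalation DLTs, none crosses the pooled boundary without also crossing Section 3's. The total is therefore escalation stopping plus (1 − escalation stopping) × Section 3 stopping:

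- 0.10: 0.135 + 0.865 × 0.303 = 0.397
- 0.20: 0.423 + 0.577 × 0.584 = 0.760
- 0.30: 0.695 + 0.305 × 0.794 = 0.937

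After 0/10 or 1/10 the pooled rule also never fires first. It can only after 2/10, when the first two expansion women both have DLTs.

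**Step 6. Does a pooled reading of the 30% reconcile the texts?** No. It gives 4/13, 5/14–16 and 6/17–20, which differs from Section 13.4 at n = 14 (5 against 4) and n = 17–19 (6 against 5).

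**The case against.** The best counter-argument is that the two sentences do not contradict each other. Each is a sufficient condition to stop, neither says to continue below its boundary, and a team can comply with both by stopping at whichever is met first. That reading is available and is the safe one, but the protocol does not state it. It also makes the pooled rule idle: from 0/10 it can never stop the trial before Section 3 does. And the 15%, 51% and 82% given for the level would then no longer describe the protocol as a whole, although they remain right for the boundaries listed beside them.

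Other points stand in part:

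- **Direction.** Section 3 is the more protective rule, and DSMB review, sponsor discontinuation and individual off-drug rules also apply. The fault is unclear precedence, not missing protection.
- **Likelihood.** After 0/10 a high true rate is improbable: 0/10 has probability 0.7¹⁰ = 0.028 at a rate of 0.30, and Pr(rate ≥ 0.20) is 0.009 under the protocol's prior. The practical contrast is mainly about stopping too readily at low rates.
- **The look at three.** Removing it lowers the 30% at a rate of 0.10 to 13.5%, so its marginal effect is about 17 points, less than its 27% first-crossing share.
- **Three women is the extreme case.** At about three participants a month and four weeks of follow-up, more women may have started before the third is fully evaluated. Escalation participants may also give optional biopsies.
- **Strictness.** A sponsor may choose a tighter rule for expansion than for escalation. That choice is legitimate, but it has to be stated once.

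**Conclusion.** The concern holds. Two different trial-termination rules apply to the same cohort, with no stated precedence, and they part at outcomes that could readily occur. Given 0/10, a true DLT rate of 0.10 gives a 30% chance of termination under one section and 0.1% under the other. The stated level-wide stopping probabilities are correct for the pooled boundaries but rise to 40%, 76% and 94% if Section 3 is enforced as well. A termination rule needs a single reading, so this must be fixed.

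Assumptions: DLTs are independent between women; each woman's DLT status is known before the next look; Section 3's percentage counts expansion women only, which is its natural reading; and no expansion participant has yet been counted. On the last, Section 3 reports status as of October 2019, while this protocol version is dated April 2021.

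**What to change.** Write one governing rule in identical words in Sections 3, 8.1 and 13.4. Say whether the 10 escalation participants count, cross-refer to the rule in Section 13.9, and give matching stopping probabilities at 0.10, 0.20 and 0.30. The sponsor chooses among:

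- **(A) Pooled posterior rule.** Delete the 30% sentence and its look schedule from Section 3. Keep 15%, 51% and 82% for the level, and add 0.1%, 2.0% and 10.0% for the expansion given 0/10.
- **(B) Expansion-only 30% rule.** Replace the pooled boundaries. State 30%, 58% and 79% for the expansion and 40%, 76% and 94% for the level.
- **(C) Whichever is met first.** Same totals as (B).

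Until the text is amended, stop when either trigger is met.

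The cost is wording in three sections, one cross-reference and one set of figures, with no extra participants. The figures become less comfortable: (B) and (C) disclose a 30% chance of stopping the expansion at a true rate of 0.10, and (A) discloses only a 10% chance of stopping it at 0.30 after 0/10.
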